6.2. SENSITIVITY ANALYSES

Some sensitivity analyses regarding missing data were described in Section 6.1. A complete case analysis as well as an analysis using multiple imputation will be done.

6.3. SUBGROUP ANALYSES

Exploratory subgroup analyses will be performed for the primary outcome variable with respect to the age at surgery (> 70 days vs <= 70 days), duration of surgery (< 2 hours vs >= 2 hours) and country. Stratified analyses will be done by repeating the same analysis as described in Section 5.2 for each of the above mentioned factors.

The assessment of treatment-by-country interaction will be made by fitting a model for the primary outcome variable. The model will include treatment arm, country, and gestational age as fixed effects as well as the interaction term country by treatment. The p-value for the country by treatment interaction will be presented.

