2.3. STUDY POPULATION

The planned study population comprised 660 infants of postmenstrual age 60 weeks or less, requiring inguinal hernia repair under anaesthesia. Exclusion criteria include pre-existing recognised risk factors for adverse neurodevelopmental outcome or previous exposure to general anaesthesia; or being born at less than 26 weeks gestation.

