6.1. HANDLING OF MISSING DATA

Statistical analysis approaches and imputation techniques can never compensate for or exactly reproduce missing data. Therefore, no analytical strategy exists that can minimise all bias potentially introduced by missing data. However, consistencies or inconsistencies in the results based on different strategies to handle missing data can provide support for the interpretation of the study findings and either strengthen or qualify the study conclusions.

Allowing for missing values using multiple imputation:

Assuming validity of the MAR assumption, fully conditional modelling will be used to multiply impute missing values based on variable-specific prediction models. In particular, multivariate imputation chained equations (MICE) will be used to perform imputation of missing values. Depending on the type of outcome, different link functions and model specifications will be employed to utilise the built-in imputation: predictive mean matching under a Gaussian model for continuous data, logistic regression for binary data, polytomous logistic regression for unordered categorical data and proportional odds models for ordered categorical data.

Statistical Analysis Plan

If MICE models do not converge missing values will be filled in using multivariate normal regression (MVN). These two methods have been shown to give broadly equivalent results.

A total of 20 imputed data sets will be generated based on the MICE algorithm. For each of the respective data sets, the outcome-specific effect estimate and standard error will be computed and pooled using Rubin's rules (Van Buuren, 2007).

In the analysis of the 5-year data of the GAS study, the variables used in the multiple imputation models will include baseline, post-randomisation, 2 year cognitive variables and 5 year outcome variables. The following prespecified variables will be used as predictor variables within the imputation approach (since most of these variables also have missingness, they will also be imputed where necessary):

Baseline: anaesthesia group, country, site (if possible), sex, gestational age at birth (categorised), birth weight, mother received antenatal steroids, mother's education, maternal age < 21

Surgery: need for fluid bolus for hypotension, duration of surgery, significant postoperative apnoea, age at surgery

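### SAP 6.3 examines dependence of the IQ effect on age at surgery only by separate analyses either side of 70 days; it plans no arm-by-age estimate, though age is held uncut

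*SAP*

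**What the plan says.** SAP Section 6.3 opens: "Exploratory subgroup analyses will be performed for the primary outcome variable". Age at surgery is one of three factors, with two levels, "age at surgery (> 70 days vs <= 70 days". The others are duration of surgery, also in two levels, and country. The method is: "Stratified analyses will be done by repeating the same analysis as described in Section 5.2 for each of the above mentioned factors". Section 6.3 gives no reason for choosing 70 days.

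The only interaction model in Section 6.3 is for country: "The p-value for the country by treatment interaction will be presented". There is no counterpart for age.

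Section 6.1 lists the surgical predictors for the imputation models, including "significant postoperative apnoea, age at surgery", with no cut-point attached. The variable is therefore available on a finer scale than Section 6.3 uses.

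Section 2.3 bounds the possible ages. The population is "660 infants of postmenstrual age 60 weeks or less", and the exclusions include "being born at less than 26 weeks gestation". The SAP gives neither the distribution of age at surgery nor the share of infants on each side of 70 days.

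**The concern.** Two features of Section 6.3 limit what it can say about age.

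- **The cut.** Infants aged 69 and 71 days fall in different groups, while infants aged 10 and 69 days count as the same. A trend within either group cannot be seen.
- **No contrast.** Separate analyses give two arm differences with two intervals. They give no estimate, and no interval, for how the arm difference changes with age.

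The stake is interpretive. In an equivalence trial, two strata that look alike are easily read as showing that the effect does not depend on age. A coarse comparison without an interval makes that reading easier than the data may justify. Under Section 6.4 a continuous-age model added later would have to be identified as unplanned, so it is better prespecified now.

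**Working it through.** **Reproducing the plan's own figure.** The SAP states no power or information figure for the age subgroup, so only the overall size can be checked. Section 2.4 gives margin 5, true difference 1, SD 15, 90% power and a two-sided 95% interval. The one-sided normal formula gives 2 × 15² × (1.960 + 1.282)² / (5 − 1)² = 296 per arm, or 592 in total, within 3% of the stated 598. At 299 per arm the two-sided equivalence formula gives 90.2% power. The planned 660 less 10% is 594, used below.

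**Range of ages.** Counting age from birth, the limits in Section 2.3 allow up to about 60 − 26 = 34 weeks, or 238 days. The younger stratum thus pools 0–70 days and the older one pools 71 to about 238.

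**Information kept by the cut.** Suppose the arm difference changes linearly with age. The fraction of information on that trend kept by the indicator of age > 70 days is the squared correlation between age and the indicator. With p the share of infants at or below the cut:

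- normal age: φ(z_p)² / [p(1 − p)], where z_p is the normal quantile at p
- uniform age: 3p(1 − p)
- skewed ages: computed numerically

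| Assumed age distribution | Split | Kept | Lost |
|---|---|---|---|
| Normal, centred on 70 days | 50/50 | 0.64–0.65 | 35–36% |
| Gamma, mean 70 days | 43% above 70 | 0.62 | 38% |
| Uniform, 10–200 days | p = 60/190 = 0.316 | 3 × 0.316 × 0.684 = 0.65 | 35% |
| Uniform, 0–238 days | p = 70/238 = 0.294 | 3 × 0.294 × 0.706 = 0.62 | 38% |
| Uniform, cut at median | 50/50 | 3 × 0.5 × 0.5 = 0.75 | 25% |
| Normal | 30/70 | 0.58 | 42% |
| Normal | 20/80 | 0.49 | 51% |
| Right-skewed shapes, cut at median | 50/50 | 0.48–0.59 | 41–52% |

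In the first row, 0.64 is the exact normal value (0.637); the slightly higher figure arises when the normal is cut off at birth. Very uneven splits can lose more than any row shown.

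**What that means for an interaction test.** With N = 594, SD 15 and 1:1 allocation, the standard error of the interaction per SD of age is 15 / √(594/4) = 1.23 points. A change of 3.45 points in the arm difference per SD of age then has 80% power with age continuous. For a normal age cut at its median, the cut acts like 594 × 0.637 = 378 infants, and power is Φ(3.45 × √0.637 / 1.23 − 1.96) = 61%. The 3.45 was chosen to give 80%; it has no source in the SAP.

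**If the truth is a step.** If the arm difference jumps at 70 days and is flat on either side, the two-level factor loses nothing. Because the squared correlation is symmetric, a linear term would then keep only the fraction in the "Kept" column.

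**The case against.** The strongest reply is that nothing here is an error. Section 6.3 calls these analyses exploratory and fixes a single cut in advance, so it cannot be chosen from the 5-year results. The equivalence rule in Section 5.2 and the sample size in Section 2.4 do not depend on it. The SAP gives no reason to expect a linear shape, and a linear term loses power if the truth is a step; a spline check does not restore that power. All of this stands. It sets the weight of the point, but does not supply the missing arm-by-age estimate.

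A reader might infer several stronger things that the SAP does not support:

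- **That the split discards about a third of the information, as a fact.** The figure needs a linear trend and an assumed age distribution, and the SAP gives neither.
- **That the planned analysis has about 61% power.** That power belongs to a two-level interaction test, which Section 6.3 does not contain. Moreover, 3.45 points per SD means a change of 6.9 points from one SD below to one SD above the mean age, more than the 5-point margin.
- **That age is complete for every infant.** Section 6.1 says most of the imputation predictors have missing values and does not exempt age at surgery.
- **That age is the main modifier, or that equivalence will be claimed at all ages.** Section 6.3 does not rank its three factors, and the SAP announces no such claim.

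**Conclusion.** The point holds as a low-cost improvement. Section 6.3 examines effect modification by age at surgery only through separate analyses either side of 70 days and gives no estimate of how the arm difference changes with age, while Section 6.1 shows that uncut age is held.

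The size is conditional. Under a roughly linear trend the loss is about 35–38% for the three distributions named first in the table, and 25% to over 50% across other plausible shapes and splits. It is zero for a step at 70 days. The absence of an arm-by-age estimate does not depend on any of these assumptions.

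It would go too far to call the exploratory split invalid or to say it threatens the trial's conclusion: the primary equivalence conclusion is unaffected.

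**What to change.** In Section 6.3, keep the 70-day split for display and add one prespecified exploratory model: the Section 5.2 model plus age at surgery in days and arm × age, linear, with a spline check of the shape. Report the interaction with its 95% CI and the fitted arm difference at the quartiles of age.

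In Section 6.1, carry the arm × age structure into the imputation model, for example by imputing separately by arm. The primary method uses multiple imputation, and imputing IQ without this term would pull the interaction towards zero. This is in line with the commitment in Section 6.1 to keep the variables needed for congeniality with the analysis models.

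The cost is one extra exploratory model, a matching imputation term and a few sentences of text. The downside is the linear shape assumption, which loses power if the true effect is a step; the retained split still shows that pattern.

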2.4. SAMPLE SIZE

The sample size was based on the 5 year follow up neurodevelopmental outcome. The WPPSI-III full scale IQ score is a standardised score with a mean of 100 and standard deviation of 15. A difference of 5 points (1/3 of a standard deviation) will be taken as the largest difference that would be acceptable to demonstrate equivalence.

The planned sample size was chosen so that if the two methods of anaesthesia really were equivalent and we assumed an expected difference of only 1 standardised score point, there was a 90% chance that a 95% confidence interval will exclude a difference of more than 5. With these assumptions, the trial would need 598 infants in total. The planned sample size of 660 allowed for 10% loss to follow-up. The enrolment target was increased to enable replacement of participants who were excluded due to major protocol violations.

Statistical Analysis Plan

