3.2. PROTOCOL VIOLATIONS

Major protocol violations include:

- surgery cancelled
- · received any sevoflurane or other volatile anaesthetic agents if allocated to awake RA arm
- received any other sedative agent if allocated to awake RA arm

Minor protocol violations include:

- variations in local anaesthetic agent
- use of opioids and/or nitrous oxide if allocated to the GA arm
- variations in volatile anaesthetic agent if allocated to the GA arm
- assessed at an age outside the planned window at 5 years

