5.2. ANALYSES OF PRIMARY OUTCOME VARIABLE

Descriptive summary statistics for the primary outcome variable at 5 years chronological age will be reported.

Version 1

Statistical Analysis Plan

Linear regression will be used to analyse the Full Scale IQ score of the WPPSI-III at 5 years. The model will include the factor variables anaesthesia arm (factor levels: GA and RA), gestational age at birth (factor levels: "182 to 209 days", "210 to 258 days" and ">= 259 days") as fixed effects and site as a random effect. If the model does not converge (e.g. because of small numbers in some sites) consideration will be given to replacing site in the model with country as a fixed effect.

The analysis will be conducted for the PP and the ITT populations. The analyses will be repeated for the subset of participants with follow-up data at 5 years as well as using multiple imputation to handle the cases lost to follow-up under the MAR assumption. The primary analysis will be based on the PP population and the multiple imputation analysis method because this is an equivalence study. A PP analysis is likely to give a more conservative estimate (in the direction of non-equivalence) of the true causal effect.

The model coefficient for the anaesthesia treatment effect (conditional mean difference) will be computed along with a two-sided 95% confidence interval. Equivalence will be accepted if this confidence interval excludes values less than -5 points and values greater than +5 points.

Loss to follow-up will be investigated by providing a table with summary statistics by treatment arm for participants who attended and did not attend the 5 year visit. Variables included in this table will include key baseline variables as well as the composite cognitive, language, motor and social-emotional score of the Bayley scales of infant and toddler development measured at the 2-year time point.

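### Subgroup plan: age and duration of surgery are examined only by separate within-stratum analyses, and duration of surgery is a post-randomisation factor

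*SAP*

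**What the plan says.** SAP Section 6.3 labels the subgroup analyses exploratory and restricts them to the primary outcome. The factors are age at surgery, split at 70 days, and "duration of surgery (< 2 hours vs >= 2 hours) and country". The method is given in one sentence: "Stratified analyses will be done by repeating the same analysis as described in Section 5.2 for each of the above mentioned factors".

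The second paragraph of Section 6.3 adds one model with arm, country, gestational age and a country-by-arm interaction, and promises the interaction p-value. No such model is planned for age at surgery or duration of surgery.

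Section 5.2, which is to be repeated, contains the regression model, the PP and ITT versions, the complete-case and imputed versions (PP with imputation being primary), and the decision rule: "Equivalence will be accepted if this confidence interval excludes values less than -5 points and values greater than +5 points".

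On timing, Section 2.1 says that infants entered the trial before their operation. The imputation list in Section 6.1 puts duration under a surgery heading, apart from the baseline variables: "need for fluid bolus for hypotension, duration of surgery, significant postoperative apnoea". Section 3.2 makes it a major violation, and so a reason for removal from PP, if a child "received any sevoflurane or other volatile anaesthetic agents if allocated to awake RA arm" or received any other sedative agent in that arm.

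**The concern.** There are three linked weaknesses.

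1. **No direct comparison of effects for age and duration.** A reader given one estimate and interval per stratum will compare them by eye. Strata with the same true effect can easily fall on opposite sides of the margin, and the plan supplies no estimate of the difference between strata to set against that impression.
2. **Duration of surgery is not a baseline factor.** It is realised after allocation and could be influenced by the anaesthetic technique. Splitting on it can put different kinds of children into the two arms of a stratum. The stratum of 2 hours or more is also the one most likely to be read as evidence on long exposure.
3. **The margin may travel with the method.** If all of Section 5.2 is repeated, so is the ±5 rule, in strata that may be too small to satisfy it whatever the true effect.

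At stake is how the exploratory results are read. The trial's primary conclusion does not depend on them.

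**Working it through.** **Inputs (SAP).** Margin ±5 (Section 5.2). From Section 2.4: "The WPPSI-III full scale IQ score is a standardised score with a mean of 100 and standard deviation of 15"; a true difference assumed to be 1 point; for power and confidence level, "there was a 90% chance that a 95% confidence interval will exclude a difference of more than 5"; 598 children needed and 660 planned. From Section 2.1: 1:1 allocation and seven countries.

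**Reproducing the plan's figure.** n per arm = 2 × 15² × (1.96 + 1.2816)² / (5 − 1)² = 450 × 10.51 / 16 ≈ 296, or 592 in total, close to the stated 598. With both limits taken into account, SE = 30/√598 = 1.227 and power = Φ(4/1.227 − 1.96) − Φ(−6/1.227 + 1.96) = 90.2%. The SAP's inputs are therefore consistent and can be carried into the strata.

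**Two equal halves (assumed split; 299 children each).**
- SE = 30/√299 = 1.735.
- Power to meet ±5 in one half, true difference 1: Φ(4/1.735 − 1.96) − Φ(−6/1.735 + 1.96) = 0.635 − 0.067 = 0.568.
- Probability that the halves disagree although the true effect is the same in both: 2 × 0.568 × 0.432 = 0.49. With a true difference of 0 the pass rate is 0.643 and the disagreement probability is 2 × 0.643 × 0.357 = 0.46.

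**The direct comparison on the same data.**
- SE of the difference in effects = 30 × √(1/299 + 1/299) = 2.45, so the 95% CI is ±4.8.
- Power for a 5-point interaction: Φ(5/2.45 − 1.96) = 53%. With a 10%/90% split it is 23%.
- The interaction estimate is imprecise, but its interval shows that imprecision. A pair of separate verdicts hides it.

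**The ±5 rule in small strata.**
- Half-width = 1.96 × 30/√N. It is below 5 only if N > (1.96 × 30/5)² = 138.3, so at least 139 children (70 per arm with exact balance).
- Equal countries: 598/7 = 85 gives 6.4; 660/7 = 94 gives 6.1. Both exceed 5, so the rule fails even with an observed difference of 0.
- Section 2.4 says the enrolment target was raised but not by how much. Taking 720 or 800 as assumed totals, the half-width is still 5.8 or 5.5.
- Using t quantiles, an average country could pass only with a residual SD of about 11.6 (N = 85) to 12.2 (N = 94) or lower.
- If a two-level factor puts 20% of 598 children in one stratum (about 120), the half-width there is 5.4; with 10% (about 60) it is 7.6.

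All of these figures ignore covariate adjustment and the extra variance from imputation.

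**Duration: reasoning from the text.** Allocation precedes the operation, so its length is a consequence of what happens afterwards. ITT keeps every child in the allocated arm, but membership of a stratum is itself set after allocation. If arm affects duration, the two arms of the same stratum are not comparable. PP could add selection: children in the RA arm who received volatile or sedative agents leave the set, while no rule in Section 3.2 removes a child in the GA arm because the operation was long.

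**The case against.** The strongest reply is that these analyses are labelled exploratory, that no primary or secondary conclusion rests on them, and that Section 6.3 does plan an interaction test. That limits the weight of the point. It does not supply the missing interaction for age and duration, nor does it make duration a baseline factor.

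A reader might infer more than the SAP supports in five ways:

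- *That no subgroup is tested for effect modification.* This is wrong for country. The only gap there is that a p-value is promised without the differences or intervals behind it.
- *That the SAP will declare equivalence subgroup by subgroup.* No sentence says so. It follows only from a literal reading of repeating Section 5.2; repeating just the model and interval is an equally natural reading.
- *That no country could meet ±5.* Country sizes are not given. A country with about 139 children or more could pass, as could a smaller one with a lower SD. Nor does the result extend to an evenly split two-level factor, where power is about 57%.
- *That the stratum of 2 hours or more is confounded.* The SAP has no data on whether RA children given volatile or sedative agents cluster in long operations, and the ITT version retains them. The split could be confounded; that it will be is not shown.
- *That the Section 6.1 list settles the status of duration.* The same line contains age at surgery, and the list only names imputation predictors. Timing is what matters: operation length can respond to the technique, whereas age at a planned operation has little room to do so.

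**Conclusion.** The point holds in a limited form. For age and duration of surgery, Section 6.3 specifies a method that cannot show whether effects differ. With equal halves, SD 15, 598 children and a true difference of 1, separate ±5 verdicts would conflict about 49% of the time with no effect modification at all. Equal halves are an assumption, since the actual splits are not stated. The duration split is unprotected by randomisation in both PP and ITT; the size of any resulting bias cannot be derived from the SAP. The small-country result (half-width 6.1 to 6.4 for 85 to 94 children) is arithmetically firm but depends on SD 15, equal country sizes and a literal reading of the cross-reference to Section 5.2. This is a cheap improvement to exploratory analyses and no threat to the primary analysis.

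**What to change.** Amend Section 6.3 as follows.

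- **Age at surgery:** fit one model on all children with an arm-by-age-group interaction, and report the difference in effects with its 95% CI beside the stratum estimates.
- **Country:** keep the planned interaction model and report country-specific effects with 95% CIs beside the p-value. Taking these from one model also avoids refitting Section 5.2 inside a single country, where its fallback of replacing site with country has no meaning.
- **Duration of surgery:** drop it as a treatment-effect subgroup, or keep it with an interaction estimate and label it a non-randomised, descriptive comparison. A pre-randomisation substitute would be preferable in principle, but the SAP does not show that a suitable one was recorded. Planned unilateral versus bilateral repair, for example, appears only in the description of eligible infants.
- **All subgroups:** state that the ±5 equivalence rule is not applied within them.

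The cost is a few sentences and one additional model, or two if duration is kept. If the interactions are estimated after multiple imputation, the imputation model should carry the same terms, in line with the congeniality commitment in Section 6.1. The real loss is that the 2-hour contrast can no longer be presented as a randomised comparison.

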2. BACKGROUND/INTRODUCTION

2.1. STUDY DESIGN

The study is a prospective, observer blind, multi-site, randomised, controlled, equivalence trial. There are a total of 28 sites from seven countries. Participants are randomised in a 1:1 ratio to receive either regional anaesthesia (RA) or general anaesthesia (GA) during surgery for hernia repair. Randomisation is stratified by gestational age at birth and by site, giving a total of 52 strata.

Participants are infants scheduled for unilateral or bilateral inguinal hernia repair at one of the participating sites, identified through review of planned theatre schedules. The duration of participation was five years. Infants were enrolled before surgery. Data were collected before and during anaesthesia and in the early post-operative period (up to 5 days following the surgery). Formal neurodevelopmental assessments occurred at 2 years corrected age and 5 years chronological age.

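### The country-by-treatment interaction model in SAP Section 6.3 leaves out site, so the exploratory test is mildly conservative if sites within a country differ in mean IQ

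*SAP*

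**What the plan says.** - **Design (SAP Section 2.1).** "Randomisation is stratified by gestational age at birth and by site, giving a total of 52 strata". The same section states: "There are a total of 28 sites from seven countries". Allocation is 1:1.
- **Primary model (SAP Section 5.2).** Anaesthesia arm and gestational age enter "as fixed effects and site as a random effect". If that model does not converge, "consideration will be given to replacing site in the model with country as a fixed effect". Country therefore stands in for site only on that condition.
- **Country subgroups (SAP Section 6.3, first paragraph).** The exploratory stratified analyses, including those by country, repeat the Section 5.2 analysis, so they carry site.
- **Country interaction (SAP Section 6.3, second paragraph).** "The model will include treatment arm, country, and gestational age as fixed effects as well as the interaction term country by treatment". An interaction p-value is to be presented. Site is absent, no convergence condition is attached, and no reason is given. Gestational age, the other stratification factor, is kept.

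**The concern.** The country-specific estimates and the p-value that compares them come from differently specified models within one section. The estimates are adjusted for site and the test is not.

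The statistical consequence is a familiar one. When arms are balanced within site, differences in mean IQ between sites cancel out of each country's treatment contrast, so they do not add to its true variance. A model without site still counts those differences as residual noise. The standard errors of the interaction terms are then too large and the test rejects too seldom.

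This is the only interaction p-value that the SAP specifies. Age at surgery and duration of surgery get stratified analyses only. In an equivalence trial a non-significant country interaction reads as reassurance, so a tilt towards non-significance is better avoided when avoiding it costs almost nothing.

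**Working it through.** **Inputs from the SAP.** There are 28 sites and 7 countries, so the interaction has 7 − 1 = 6 degrees of freedom. Allocation is 1:1 and the SD is 15 (Section 2.4). The number needed for analysis is 598 (Section 2.4).

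**Inputs assumed.** The within-country site ICC is not given, so a range is shown. The simulation also assumes 8, 7, 5, 3, 2, 2 and 1 sites per country, uneven site sizes, gestational-age shares of 10/45/45%, and complete data.

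**Step 1: the plan's own figure.** The SAP gives no size or power for the interaction test. Its sample size can be checked: 2 × (1.960 + 1.282)² × 15² / (5 − 1)² = 295.5, so 296 per arm and 592 in total. The stated 598 is within about 1% of this and gives 90.2% power. The figure is sound and serves here only to set the sample size.

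**Step 2: standard errors.** With balance within site, the true variance of a country's treatment contrast is proportional to (1 − ICC), while the model without site estimates it as if it were proportional to 1. The inflation factor is 1/√(1 − ICC).

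**Step 3: size by formula.** The 5% critical value of chi-squared on 6 degrees of freedom is 12.592. The true size without site is P(χ²₆ > 12.592/(1 − ICC)). At ICC 0.10, for example, 12.592/0.90 = 13.99 and the tail probability is 3.0%.

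**Step 4: simulation.** The 6-degree-of-freedom F test was run 2000 times per setting, with and without a site random intercept. Power is for assumed country effects alternating between +4 and −4 points.

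| ICC | SE inflation | Size by formula, no site | Simulated size, no site / with site | Simulated power, no site / with site |
|---|---|---|---|---|
| 0 | 0% | 5.0% | 5.4 / 5.4% | 67 / 67% |
| 0.02 | 1.0% | 4.6% | 3.8 / 4.2% | 66 / 67% |
| 0.05 | 2.6% | 3.9% | 4.4 / 4.8% | 67 / 70% |
| 0.10 | 5.4% | 3.0% | 3.6 / 5.7% | 63 / 69% |
| 0.20 | 11.8% | 1.5% | 2.2 / 4.7% | 66 / 76% |

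Simulation error is about 0.5 points for size and 1 point for power. The site model was given the true ICC, so its gains are upper bounds. The formula overstates the conservatism somewhat, because the country effects absorb part of the site variation.

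A separate simulation with 598 infants, 28 sites and 7 countries, in a lower-power setting, gave size 3.9 v 5.1% and power 29 v 33% at ICC 0.10 (without v with site). The gain was about 1 to 2 power points at ICC 0.02 to 0.05.

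**Step 5: does the direction hold?**
- With balance within site and any ICC above 0, the p-value without site was the larger one in at least 99% of runs.
- With an assumed 18% random loss from the regional arm, it was the larger one in 86 to 90% of runs (ICC 0.05 and 0.10).
- With treatment effects varying between sites within a country (SD 2 or 4 points, ICC 0.05) and no country effect, the model without site rejected in 6.3% or 16.6% of runs. With a site intercept the figures were 7.4% and 18.4%. The p-value is then too small under either model.

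**The case against.** A reader might infer that the heterogeneity p-value is certainly too large, that real country differences will be missed, and that pooling is thereby wrongly supported. The case against that reading is strong on four counts.

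- **It rests on an unknown.** The SAP gives no between-site variance, and country effects already remove the between-country part. At an ICC of 0.02 to 0.05 the difference is close to negligible.
- **The direction is not assured.** Two of the three major violations in Section 3.2 can occur only in the regional arm, and the primary analysis in Section 5.2 is per protocol. Exclusions can therefore disturb balance within site. If treatment effects vary by site, the error reverses and a site intercept does not repair it.
- **The test carries no decision.** Section 6.3 calls these analyses exploratory and only presents the p-value. Equivalence is decided in Section 5.2 by the confidence interval, and the country-stratified analyses give further evidence on heterogeneity.
- **Country in place of site is a form that the plan accepts elsewhere.** The interaction model is the Section 5.2 fallback plus one term.

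The first three stand, and they limit the point to a conditional and modest one. The fourth stands only in part: the fallback in Section 5.2 is tied to non-convergence, and Section 6.3 states no such condition. None of the four gives a reason for leaving site out. Variation in treatment effects between sites is a separate problem.

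**Conclusion.** The point holds in a limited form. Section 6.3 drops from its interaction model a stratification factor that both Section 5.2 and the country-stratified analyses keep. That can be read from the text without any assumption.

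The numerical effect is conditional on sites within a country differing in mean IQ and on arms staying roughly balanced within site. Under an assumed ICC of 0.02 to 0.10, the true size is roughly 3 to 4.5% by formula (about 4% at 0.10 in simulation) instead of 5%, with about 1 to 7 points of power lost. At an ICC of 0 there is no loss.

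The document does not support a claim that country differences will be under-detected as a matter of course, or that the equivalence conclusion is at risk. This is a small improvement to an exploratory analysis.

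**What to change.** In Section 6.3, add site as a random intercept to the country-by-treatment interaction model, keeping treatment arm, country, gestational age and the interaction as fixed effects. Use country alone only if that model does not converge, under the same rule as Section 5.2. If site is left out on purpose, say why.

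The cost is one term in one model, already specified elsewhere in the SAP. The only practical risk is non-convergence, which the fallback covers. The text should not present the site intercept as protection against treatment effects that differ between sites within a country.
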